1.3. STUDY SETTING

The trial was conducted at two tertiary institutions that are affiliated to the University of Zimbabwe. These serve as referral centres for 12 local authority clinics located in Harare as well as district and provincial hospitals in the surrounding provinces: Harare Central Hospital i.e. Harare Maternity Hospital (HMH) and Parirenyatwa Group of Hospitals i.e. Mbuya Nehanda Maternity Hospital (MNMH). Most of the patients understood at least one of either English or Shona languages.

Located in the Southerton suburb, HMH is the referral centre for pregnant women mainly from the southern and western suburbs of Harare. The unit has an Antenatal Ward (ANW), Labour Ward (LW), Early Labour Ward (ELW), Post Natal Ward A (PNA) for patients after vaginal delivery and Post Natal Ward B (PNB) for patients post caesarean delivery. Babies with complications are admitted in the Neonatal Unit (NNU).

The northern and eastern suburbs are served by MNMH which is located in Avondale suburb. The unit has an ANW, a LW, Post Caesarean Section Ward (PCW) and a Postnatal Ward (PNW). Ill babies are admitted in the Neonatal Intensive Care Unit (NICU).

There are five teams with 3 to 4 consultants each at MNMH and 5 teams at HMH each with 2 to 4 consultants. MNMH delivers a total of 535 pregnancies per month while HMH delivers 1,335. On average 60 elective and 250 emergency caesarean sections are done at HMH per month, while 80 elective and 210 caesarean deliveries on average are done at MNMH. Refer to C in **Error! Reference source not found..**

Elective caesarean sections are performed by Senior House Officers and Registrars (including the principal investigator) mainly, with some cases performed by Senior Resident Medical Officers (in their second year of internship) or Consultants (usually in cases that have complications or serious concurrent medical/obstetric indications).

1.4. SAMPLE SIZE

The sample size was calculated assuming a proportion of 2.1% PPH in the experimental group and 5.8% in the control group ⁽³⁸⁾ at 95% confidence interval and 90% power using the Fleiss formula giving a minimum sample size of

$$\begin{aligned} n &= \frac{[Z_{\alpha/2}\sqrt{(r+1)\bar{p}\bar{q}} + Z_{\beta}\sqrt{rp_1q_1 + p_2q_2}]^2}{r(p_1 - p_2)^2} \\ &= \frac{[1.96\sqrt{(1+1) \times 0.0395 \times 0.9605} + 1.28\sqrt{0.021 \times 0.979 + 0.058 \times 0.942}]^2}{(0.021 - 0.058)^2} \\ &= 581 \text{ per group} \end{aligned}$$

Thus, total minimum sample size $N = 1,162$ women

Where: n = sample size

$Z\alpha = 1.96$ at 95% confidence interval

$\alpha = \text{probability of a type I error (significance level)} = 0.05$

$\beta = \text{probability of a type II error (1 - power of test)}$

$p_1 = \text{proportion of PPH in the experimental group} = 0.021$

$p_2 = \text{proportion of PPH in the control group} = 0.058$

$r = \text{ratio of control group/population 2 to experimental group/population 1}$

$q = 1-p$

1.5. RECRUITMENT AND ALLOCATION

Women who satisfied the inclusion criteria were provided with information about the trial in a language they understood by the researcher or research assistants.

Informed consent was signed on the day before elective caesarean section.

They were randomized to either the group that received TXA or the group which did not receive TXA. There was no blinding of staff or the patient.

1.6. RANDOMIZATION

A randomized allocation to study and control groups using computer-generated random numbers was done by the trial statistician.

Equal numbers were randomly allocated to the two groups for the two hospitals.

Based on the sample size the plan was for the statistician to prepare random numbers for 1,162 patients. Half of these numbers were labelled with A which represented the intervention 10mg/kg TXA and oxytocin 5IU e.g. random number 4A, represented random number 4, allocated to group A. The other half had the extension B (control group) to receive Oxytocin 5IU only.

The computer-generated numbers assigned the trial group and also a unique participant number. The numbered folded slips of paper were placed into sealed identical envelopes by the principal investigator. The sealed envelopes were kept in a box at each hospital in a locked-up room. At the beginning of the trial, TXA for 200 patients was available. The statistician therefore initially prepared random numbers for 400 patients (200 with the extension A and 200 with the extension B), half of which were prepared for HMH (1 – 200) and the other half for MNMH (1 – 200). A further 106 were prepared when the 400 numbers were used up to make the total number recruited 506 during the initial trial period.

The patients were enrolled by the principal investigator or the research assistants on the day before their scheduled caesarean section. Once they met the study criteria per the screening tool (see **Error!**

Reference source not found.), informed consent was obtained (**Error! Reference source not found.** & **Error! Reference source not found.**). The participant was asked to pick an envelope from the box. The envelope would then be opened by either the participant or the researcher.

The study number would then be entered on the data collection tool as the study serial number. A unique study sticker labelled 'Group A' / 'TXA' or 'Control' would be attached to the patient's notes. The data tool would then be inserted into the notes together with a prescription form if in group A for the attention of the theatre staff and anaesthetists. (Refer to **Error! Reference source not found.**). Only the data tool was attached to the control group patient's notes. (**Error! Reference source not found.**). A list matching the serial number to the allocated group was compiled to match the original randomization.

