1.1. RESEARCH DESIGN

Open-label parallel randomized control trial in which women included in the trial were assigned either TXA or no TXA. No changes were made to the trial design after commencement.

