1.8. INTERVENTION

The participants in the intervention arm received TXA (10mg/kg) administered slowly over 5 minutes intravenously (iv) 10 minutes prior to skin incision and prophylactic oxytocin (5 IU iv) slow administration by the anaesthetists on delivery of the baby. Participants in the control group received prophylactic oxytocin (5 IU iv) only on delivery of the baby. 5IU of Oxytocin were administered slowly intravenously as recommended by the WHO in 2012 ⁽¹²⁾. Updated recommendations were then published by WHO in 2018

after ethical approvals had been obtained and came to the attention of the principal investigator after the initial planned period of data collection (1 January 2018 to 31 December 2018) recommending the use of 10IU of oxytocin in the third stage. No change was made to the protocol during the data collection period⁽³⁾. All patients continued to receive 5IU of prophylactic oxytocin.

TXA (10mg/kg) solution for injection from the vial was diluted with 100 – 200ml electrolyte solution such as Normal Saline, Ringers Lactate solution, dextrose/water for injection on the same day it was to be used by the anaesthetist at the dose prescribed. Intravenous administration at a rate of 100mg or fraction thereof over at least 1 minute – usually at least 5 minutes for each patient was done. The administration was to be done at least 10 minutes before skin incision^(32, 33, 37, 38).

No additional prophylactic uterotronics were to be administered to the patient based on the anaesthetist's or surgeon's subjective preferences. Several local surgeons routinely add misoprostol for select cases at caesarean section. A recent local unpublished study conducted in 2017 concluded that adding misoprostol to the routine prophylactic oxytocin did not reduce the occurrence of PPH in patients undergoing low risk elective caesarean section⁽⁵¹⁾. Therefore, additional uterotronics were to be administered only if clinically indicated.

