1.11. STATISTICAL METHODS

Data analysis was conducted using Stata v15 (Stata Statistical Software: Release 15. College Station, TX: StataCorp LLC) following the CONSORT guidelines for reporting RCTs⁽⁵⁵⁾.

The primary analysis compared women given a low dose of TXA (10mg/kg) administered 10 minutes before elective caesarean section with prophylactic oxytocin administration to those given prophylactic oxytocin alone.

Baseline characteristics were compared between the groups to check the adequacy of randomization. Differences between patients lost to follow-up and included patients were also assessed. The intention-to-treat analysis was followed. This is a statistical concept whereby every participant in the study is accounted for in the analysis according to the randomization treatment assignment regardless of whether there is noncompliance, protocol deviations, withdrawal from the study, and anything happens after randomization⁽⁵⁶⁾.

Categorical data were reported using frequencies and proportions while continuous data were summarized using means and standard deviations for normally distributed data, and medians and quartile range where data was not normally distributed. Comparisons for categorical data were done using the chi-square test or Fisher's exact test when the sample size was small.

For continuous data, the t-test was used to compare differences between the groups and the analysis of variance (ANOVA) was used for comparing more than two groups. Where data were not normally distributed, the nonparametric Kruskal Wallis test was used to compare differences in continuous outcome for more than two groups. The Mann-Whitney U test was used to compare two groups where data were not normally distributed. Effect estimates were presented with relative risk measures and associated 95% confidence intervals. Any subgroup analysis was conducted as the primary analysis.

An analysis was conducted after 506 participants had been recruited to check if there are any significant differences in adverse events in the two groups.

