3.16. INDEPENDENT DATA AND SAFETY MONITORING BOARD

An Independent Data and Safety Monitoring Board (DSMB) was established for the study comprising of 3 individuals: Professor [name] (Statistician), Dr [name] (Obstetrician & Gynaecologist), and Dr [name] (Obstetrician & Gynaecologist).

The DSMB was established to assess at intervals the progress of the clinical trial, the safety data, and the critical efficacy endpoints, and to recommend to the sponsors and researchers whether to continue, modify, or stop the trial. The DSMB reviewed the analysis prepared for this report.

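### The 90% power belongs to 1,162 women; the only recruited total given is 506, not labelled interim or final, and a PPH comparison on it would have about 57% power or less

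*Combined protocol and SAP*

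**What the plan says.** All references are to the combined protocol and SAP, Chapter 3 unless stated.

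- **Section 1.4 (Sample Size)** assumes PPH in 2.1% of women on tranexamic acid (TXA) and 5.8% of controls. It works "at 95% confidence interval and 90% power using the Fleiss formula giving a minimum sample size of" 581 per group, 1,162 in total.
- **Section 1.6 (Randomization)** repeats the target: "Based on the sample size the plan was for the statistician to prepare random numbers for 1,162 patients". It then explains that drug for 200 women was in hand at the start, so 400 numbers were issued first, and continues: "A further 106 were prepared when the 400 numbers were used up to make the total number recruited 506 during the initial trial period".
- **Section 1.11 (Statistical Methods)** describes one analysis at that count: "An analysis was conducted after 506 participants had been recruited to check if there are any significant differences in adverse events in the two groups". It also says of the analysis in general: "Effect estimates were presented with relative risk measures and associated 95% confidence intervals".
- **Section 1.1 (Research Design)** states: "No changes were made to the trial design after commencement".
- **Section 1.8 (Intervention)** gives calendar year 2018 as an initial window for data collection.
- **Section 3.16 (DSMB)** says the board reviewed the analysis behind the report, giving neither its sample size nor its content. The board's remit is "to assess at intervals the progress of the clinical trial, the safety data, and the critical efficacy endpoints".
- **Section 2.3 (Justification, Chapter 2)** sets the aim of an adequately powered population.

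No section gives another recruited total, calls 506 interim or final, or revises the sample size or the power.

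**The concern.** The reader is given one power figure and one recruited total, and they do not belong together. Because the design is said not to have changed, the natural assumption is that 1,162 women and 90% power still describe the trial. The methods are in the past tense and speak of a completed primary comparison, yet no sample size other than 506 is documented.

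If PPH was reported on 506 women, a non-significant result read beside a stated 90% power could be taken as evidence against the planned effect. An analysis of that size would miss the planned effect more than four times in ten. The aim of an adequately powered trial would then not have been met for the primary outcome.

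**Working it through.** **Inputs.** p1 = 0.021, p2 = 0.058, two-sided alpha 0.05, 1:1 allocation and 90% power (section 1.4); 506 recruited (section 1.6). The split by arm is not reported, so 253 per arm is an assumption taken from the 1:1 allocation.

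**1. Reproduce the plan's sample size.** With p̄ = 0.0395:

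- √(2 × 0.0395 × 0.9605) = 0.2755
- √(0.021 × 0.979 + 0.058 × 0.942) = 0.2742
- n = (1.96 × 0.2755 + 1.28 × 0.2742)² / 0.037² ≈ 579.8 with the printed rounded z values (second decimals of the roots carried), and 580.3 with unrounded z values, hence 581.

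The plan's figure stands.

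**2. Power at each size, same formula.** Power = Φ[(0.037√n − 1.96 × 0.2755) / 0.2742].

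- n = 581: (0.8918 − 0.5399) / 0.2742 = 1.283, power 90.0%.
- n = 253: (0.5885 − 0.5399) / 0.2742 = 0.177, power 57.0%.

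506 / 1,162 = 0.435, or 44% of the target.

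**3. Sensitivity of the 57%.**

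| Setting | Power |
|---|---|
| 253 per arm, uncorrected chi-square, exact enumeration | 58.5% |
| 253 per arm, Fisher's exact or Yates-corrected chi-square | 49.9% |
| 240 per arm with outcome (assumed loss), normal approximation | 54.8% |
| 228 per arm with outcome (assumed loss of about 10%), normal approximation | 52.7% |

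Section 1.11 allows Fisher's test for small samples without defining small. Section 1.10 says haematocrit was not always available and offers a haemoglobin formula instead, so some outcome loss is possible but not quantified.

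**4. What 253 per arm could detect.** With 5.8% in controls, 80% power needs a TXA rate of about 1.2% (RR 0.21) and 90% power needs about 0.7% (RR 0.12). The plan assumes 2.1% (RR 0.021 / 0.058 = 0.36).

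**5. Precision if the planned rates were observed exactly.** Events would be 253 × 0.021 = 5.3 versus 253 × 0.058 = 14.7. SE of log RR = √(1/5.313 + 1/14.674 − 2/253) = 0.498, so the 95% CI for RR 0.36 is 0.14 to 0.96. At 581 per arm (12.2 versus 33.7 events) the SE is 0.329 and the CI is 0.19 to 0.69.

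**6. Hypothetical misreading (invented counts, not trial data).** 7/253 versus 15/253 gives RR 0.47, 95% CI 0.19 to 1.13, chi-square p = 0.08. The result is non-significant, yet the interval contains the planned 0.36.

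**7. Conditional remark on type I error.** If PPH could have been claimed at p < 0.05 at 506 and again at 1,162 (correlation √0.435 = 0.66), the overall two-sided error would be about 8.5%. If no efficacy claim or stop was possible at 506, it stays at 5.0%.

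**The case against.** The strongest reply is that 506 was a safety milestone on the way to 1,162. Section 1.11 gives that analysis an adverse-event purpose. Sections 1.6 and 1.8 use the word initial, the batches of random numbers are explained by drug supply, and section 1.4 still calls 1,162 a minimum. On that reading 90% remains the design power, section 1.1 needs no qualification, and there is nothing wrong with a design figure differing from the count at a milestone. Moreover, the text reviewed ends with the methods, so a participant flow may settle the matter elsewhere, and section 3.20 says the full protocol is held by the department. The planned relative risks and confidence intervals would also show any imprecision.

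Much of this stands. The interim reading is reasonable, and the documents do not rule it out. It does not settle the status, however: the same chapter reports in the past tense, cites an analysis prepared for the report, and gives no other sample size. Confidence intervals reduce the risk of misreading, but they do not correct a power figure that does not apply.

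Four stronger readings are tempting and are not supported:

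- **The sample-size arithmetic is wrong.** It is not; 581 reproduces.
- **The trial stopped at 506 and tested PPH there.** The text shows neither.
- **Every PPH analysis at 506 has 57% power.** The figure depends on the test, on complete outcomes and on an equal split.
- **The type I error is inflated to 8.5%.** That needs a possible efficacy claim at both looks, and neither is documented. The board's remit in section 3.16 includes efficacy endpoints, while the stopping criteria in section 3.17 concern risks and adverse effects. An efficacy stop is therefore neither excluded nor given a boundary in this text, and a rule may exist in the full protocol.

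**Conclusion.** The concern holds as a mismatch between the stated power and the only documented sample, not as a calculation error. The 90% applies to 581 evaluable women per group. At 506 women, a PPH comparison at the planned rates would have about 57% power under the assumptions of 253 per arm, complete outcomes and an uncorrected chi-square, about 50% with Fisher's exact test, and less with missing outcomes. Whether such a comparison was made cannot be determined from this text. If recruitment went on to 1,162 and the look at 506 was for safety only, the 90% stands and one clarifying statement resolves the point. If PPH was reported on 506, both the power statement and the way a null result may be interpreted must change. This should be fixed, because it affects what the trial can conclude.

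**What to change.** 1. In Sample Size and Statistical Methods, state that 90% power applies only to 581 evaluable women per group, and say whether 506 is interim or final.
2. State whether PPH was compared by group at 506. For any such result, give the power for 5.8% versus 2.1% as about 57% or lower (according to the test and the number with outcomes), do not describe it as adequately powered, and base the conclusion on the RR and 95% CI already planned, not on non-significance.
3. If 506 is final, qualify the statement in Research Design that the design did not change.
4. If recruitment continues, say that the look at 506 was for safety and that no efficacy claim was possible there, if that is so. Otherwise disclose the look, with the type I error of about 8.5% that would follow if PPH could be claimed at 0.05 at both 506 and 1,162.

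**Cost:** a few sentences and no extra participants. The power quoted for any PPH result on 506 women becomes less favourable.

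### Envelopes filled by an enrolling investigator and drawn from a box in no fixed order leave the allocation unverifiable; separately, the participant numbers are not unique across hospitals

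*Combined protocol and SAP*

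**What the plan says.** All of this is in the combined protocol and SAP, mainly section 1.6 (Randomization).

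- **Generation.** Allocation "using computer-generated random numbers was done by the trial statistician", with equal numbers per group.
- **Preparation.** "The numbered folded slips of paper were placed into sealed identical envelopes by the principal investigator". The envelopes sit in a box in a locked room at each hospital.
- **Enrolment.** The principal investigator or research assistants enrol, the day before surgery, after eligibility and consent.
- **Draw.** "The participant was asked to pick an envelope from the box", and "The envelope would then be opened by either the participant or the researcher".
- **Numbering.** "The computer-generated numbers assigned the trial group and also a unique participant number". For the first 400 numbers, however, "half of which were prepared for HMH (1 – 200) and the other half for MNMH (1 – 200"). A further 106 numbers followed, making 506; their range, hospital split and arm split are not given.
- **Records.** The number from the slip becomes the study serial number on the data tool, a group sticker goes in the notes, and a list of serial number against group is compiled.

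Elsewhere, section 1.7 (Blinding) says that nobody is blinded once the envelope is open. Section 1.9 (Pharmacy Plan) describes a register of TXA dispensed, with patient details and study number. Section 1.11 (Statistical Methods) plans a comparison of baseline characteristics as a check on randomization.

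**The concern.** In an open-label trial, concealment up to the moment of allocation is the main protection against selection bias. It needs two things: the enroller must not know the next assignment, and it must be possible to show afterwards that each woman took the assignment that fell to her. The described procedure gives fair protection on the first and little on the second. A woman's number becomes known only when her envelope is opened, so nothing fixed in advance links the next eligible woman to a particular slip. One person may prepare the envelopes, enrol the woman and open the envelope.

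The incentive to depart from a draw is not far-fetched. Section 1.1.2 suggests TXA particularly for women at high risk and names multiple pregnancy, anaemia and placenta praevia among the examples. The exclusion list in Chapter 3, section 1.2 (Participants) names none of these three, so enrolling staff could hold a view on which arm suits a given woman.

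The repeated numbers are a different matter. They bear on whether a record can be traced to one woman. The primary outcome is calculated from blood values before and after surgery (section 1.10, Assessment), so a serial number that points to two women is a weak key for linking data.

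**Working it through.** **1. The plan's own counts.** 200 A + 200 B = 400; 400 + 106 = 506 recruited; 2 × 581 = 1,162 planned; 1,162 − 506 = 656 still to come if recruitment resumes. The point does not depend on the sample-size formula.

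**2. What the described records would reveal.** Take each possible departure in turn.

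- *A slip is thrown away.* Its number never appears among the women. This shows as a gap against the statistician's list, so it is detectable.
- *An envelope is opened, returned and another drawn.* The returned slip goes to a later woman. Every number is still used once, each number still has its correct arm, and the totals are right. Not detectable.
- *Two women's slips are swapped before recording.* Same result. Not detectable.
- *The TXA register.* It is filled in after allocation and only for women dispensed TXA. After a return or swap it would record the woman who ended up with the A number, and so would agree with the other records. No equivalent is described for controls.
- *The baseline comparison.* It can show imbalance only in what was measured.

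The serial-to-group list therefore verifies number against arm. It does not verify which woman should have had the number, or when.

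**3. Could an enroller guess the next draw?** Assume each hospital's box starts with 100 A and 100 B, and someone keeps a tally. With *m* per arm, the expected number of correct guesses in 2*m* draws is *m* + (4^m / C(2m, m) − 1)/2. For *m* = 100, 4^100 / C(200, 100) = 17.75, so the result is 100 + 16.75/2 = 108.4 of 200, or 54.2% against 50% by chance. It rises to about 71% over the last ten draws. Predictability is modest overall; the weakness is the missing verification.

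**4. Repeated numbers.**

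- Bare numbers: 1–200 at each hospital gives 2 × 200 = 400 women sharing 200 numbers, or 400/506 = 79% of those recruited. Section 1.6 says the 400 were used up.
- With the A/B suffix: if the two lists are independent and each split 100/100 (an assumption), a given number has the same suffix at both hospitals with probability 0.5 × 0.5 + 0.5 × 0.5 = 0.5. The expected number of repeated codes is 200 × 0.5 = 100. Simulation gives a 95% range of 86 to 114.
- Without that assumption the count can be anything from 0 (mirror-image lists) to 200 (identical lists).

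**The case against.** The strongest reply is that real safeguards are in place. The statistician generated the numbers, the envelopes were sealed and identical, the room was locked, and consent came before the draw. A blind draw from such a box does not show the enroller what comes next, and a draw that is kept is random. The computer list still fixes which number belongs to which arm; only the order comes from the draw. Discarding a slip would be noticed, and the TXA register ties the women dispensed TXA to their numbers. All of this stands, and it narrows the point to returned, swapped or redrawn envelopes.

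On numbering, each hospital has its own box and range, so hospital plus number is unique for the first 400. The data tool may carry a hospital field; the appendices are not available here, so its absence cannot be assumed. Nothing says that blood samples were labelled by study number alone. This also stands: the repetition is harmless wherever the hospital is stored with the number.

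Three stronger readings are tempting. A reader might infer that concealment was broken, but the documents show only that adherence cannot be checked. A reader might infer that the duplicate numbers weaken concealment; they do not, because they concern record identity after the draw. A reader might also give weight to section 1.3, where caesareans are "performed by Senior House Officers and Registrars (including the principal investigator) mainly". An operating role says something about the lack of blinding, not about whether the draw was concealed.

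**Conclusion.** The point holds in a limited form and should be acted on. As described, the allocation is random if every first draw was kept, but no record would show that it was. Because the trial is unblinded on opening and one of the enrollers prepared the envelopes, this leaves a risk of selection bias that the baseline comparison can only partly address. The size of any bias cannot be derived from the documents: they give neither a rate of departures nor the risk profile of women who might be steered.

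As a separate traceability defect, the number described as unique is not unique. 400 of 506 women share 200 bare numbers, and 0 to 200 suffixed codes may repeat. The central figure of about 100 rests on independent lists split 100/100 at each hospital. No sample-size figure changes.

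**What to change.** **Further recruitment towards 1,162.** Replace the draw with opaque, sealed envelopes, numbered in sequence on the outside with a hospital prefix (for example HMH-001, MNMH-001). The trial statistician, who already holds the list, should prepare them. Open them strictly in order after consent, with the woman's study entry, date and time logged before opening.

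**The 506 already recruited.** New envelopes cannot help these women. Reconcile issued, used and unused numbers by hospital and arm against the statistician's list and the TXA register. State the range and the hospital and arm split of the further 106. Use hospital plus number as the data key. Report the lack of a verifiable allocation order as a limitation.

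**Cost.** A change of protocol wording, an envelope log, and a little preparation and logging time. No additional participants or procedures are needed, and clinical care is unaffected.
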